4.5.8 Laboratory, Biomarker, and Other Biological Samples

All samples for laboratory tests (hematology, blood chemistry, serologic tests) will be analyzed in the study site's local laboratory.

Blood samples should be obtained in fasted patients and handled appropriately. The following parameters will be utilized in the study:

- hematology (plasma): white blood cells (WBC) count, red blood cells (RBC) count, hemoglobin, hematocrit, platelet count, (relative) differential WBC count (neutrophils, eosinophils, basophils, monocytes, lymphocytes);
- blood chemistry panel (serum or plasma): albumin, alkaline phosphatase (AP), ALT, AST, direct bilirubin, total bilirubin, total protein, albumin, cholesterol, creatine kinase (CK), creatinine, triglycerides, gamma-glutamyl transferase

Pirfenidone—F. Hoffmann-La Roche Ltd

(GGT), glucose, lactic dehydrogenase (LDH), calcium, phosphorus, magnesium, potassium, sodium, urea nitrogen, uric acid;

- serologic tests (at screening only, exclusion tests): rheumatoid factor, anticyclic citrullinated peptide and antinuclear antibody titer.

Creatinine clearance

Creatinine clearance should be assessed at the Screening for eligibility confirmation using the following formula by Cockcroft-Gault (Cockcroft DW et al, 1976):

For serum creatinine concentration in mg/dL:

$$\text{CrCl (mL/min)} = (140 - \text{age (years)}) \times \text{weight (kg)} \times 1.0 / 72 \times \text{serum creatinine (mg/dL)}$$

For serum creatinine concentration in $\mu\text{mol/L}$:

$$\text{CrCl (mL/min)} = (140 - \text{age (years)}) \times \text{weight (kg)} \times 1.0 / 0.81 \times \text{serum creatinine (\mu mol/L)}$$

Pregnancy test

All women of childbearing potential will have a urine pregnancy test at the Screening and on Day 1 before start of treatment. Only women with negative pregnancy test will be included in the study. Urine pregnancy tests will be performed repeatedly at specified subsequent visits as scheduled in the [Appendix 1](#).

If a urine pregnancy test is positive, it must be confirmed by a serum pregnancy test. Women with confirmed positive pregnancy test should be immediately withdrawn from the study treatment (see [Section 5.4.3](#)). Urine pregnancy test will be performed by the investigator using test-strips with least sensitivity to human chorionic gonadotropin (hCG) of 10 mLU/mL.

The investigator can perform clinical laboratory assessments more frequently, if it is clinically indicated.

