5.1.1.5 Other Adverse Events

Dizziness

Dizziness has been reported in patients receiving pirfenidone. Patients should know how they react to the study drug before they engage in activities requiring mental alertness or coordination. In clinical studies, most patients who experienced dizziness had a single event, and most events resolved, with a median duration of 22 days.

Fatigue

Fatigue has been reported in patients receiving pirfenidone. Patients should know how they react to the study drug before they engage in activities requiring mental alertness or coordination.

Weight loss

Weight loss has been reported in patients treated with pirfenidone. There was an increase in anorexia and poor appetite but this was not consistently dose related. Investigator should monitor patients' weight, and when appropriate encourage increased caloric intake if weight loss is considered to be of clinical significance.

Risks which, were observed in the post-authorization setting:

- Angioedema
- Agranulocytosis

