5.3.5.2 Adverse Events That Are Secondary to Other Events

In general, adverse events that are secondary to other events (e.g., cascade events or clinical sequelae) should be identified by their primary cause, with the exception of severe or serious secondary events. A medically significant secondary adverse event that is separated in time from the initiating event should be recorded as an independent event on the Adverse Event eCRF. For example:

- If vomiting results in mild dehydration with no additional treatment in a healthy adult, only vomiting should be reported on the eCRF.
- If vomiting results in severe dehydration, both events should be reported separately on the eCRF.
- If a severe gastrointestinal hemorrhage leads to renal failure, both events should be reported separately on the eCRF.
- If dizziness leads to a fall and consequent fracture, all three events should be reported separately on the eCRF.
- If neutropenia is accompanied by an infection, both events should be reported separately on the eCRF.

All adverse events should be recorded separately on the Adverse Event eCRF if it is unclear as to whether the events are associated.

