5.3.5.4 Abnormal Laboratory Values

Not every laboratory abnormality qualifies as an adverse event. A laboratory test result must be reported as an adverse event if it meets any of the following criteria:

- Is accompanied by clinical symptoms
- Results in a change in study treatment (e.g., dosage modification, treatment interruption, or treatment discontinuation)
- Results in a medical intervention (e.g., potassium supplementation for hypokalemia) or a change in concomitant therapy
- Is clinically significant in the investigator's judgment

It is the investigator's responsibility to review all laboratory findings. Medical and scientific judgment should be exercised in deciding whether an isolated laboratory abnormality should be classified as an adverse event.

If a clinically significant laboratory abnormality is a sign of a disease or syndrome (e.g., alkaline phosphatase and bilirubin $5 \times$ ULN associated with cholestasis), only the diagnosis (i.e., cholestasis) should be recorded on the Adverse Event eCRF.

If a clinically significant laboratory abnormality is not a sign of a disease or syndrome, the abnormality itself should be recorded on the Adverse Event eCRF, along with a descriptor indicating whether the test result is above or below the normal range (e.g., "elevated potassium," as opposed to "abnormal potassium"). If the laboratory abnormality can be characterized by a precise clinical term per standard definitions, the clinical term should be recorded as the adverse event. For example, an elevated serum potassium level of 7.0 mEq/L should be recorded as "hyperkalemia."

Observations of the same clinically significant laboratory abnormality from visit to visit should only be recorded once on the Adverse Event eCRF (see [Section 5.3.5.3](#) for details on recording persistent adverse events).

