9.2. Adverse Events

eCRF form: “ADVERSE EVENTS”.

AEs will be reported on a per-patient basis, i.e. counting patients rather than events.

After informed consent has been obtained but prior to initiation of study drug, only serious adverse events caused by a protocol-mandated intervention should be reported.

After initiation of study drug, all adverse events will be reported until 28 days after the last dose of study drug. Additionally, for patients continuing in the rollover part of the study adverse events will be reported until Week 52.

Only treatment emergent AEs will be summarized. In the listings, however, all occurrences of the AEs will be presented. Treatment emergent AEs will be summarized per primary SOC and PT. Severity of treatment emergent AEs will be summarized separately.

Treatment-emergent AE is any reported adverse event that starts after initiation of the study therapy and up to 28 days after the last dose of study therapy.

All registered AEs will be coded using the MedDRA version 22.0 (or further updating) and tabulated in the report with grouping by primary system organ class (SOC) and preferred term (PT).

Number (percentage) of patients and number of AEs will be presented for the Treated Set in the following tables:

- All treatment-emergent AE / SAE;
- Treatment-emergent AE / SAE related to the study drug (“Is the adverse event suspected to be caused by the study drug on the basis of facts, evidence, science-based rationales, and clinical judgment?” = “Yes” including those events where assessment is missing);
- TEAE by maximum severity (Severity, CTCAE v.4.0);
- TEAE related to study drug by maximum severity (Severity, CTCAE v.4.0);
- TEAE leading to the permanent discontinuation of study drug (Action taken with IMP=“Permanently discontinued”);
- TEAE leading to death (AE with Outcome = “Death”) including TEAE related to the study drug;
- TEAE related to the study drug leading to death;
- TEAE of special interest (“Is this an adverse event of special interest?” = “Yes”);
- Non-serious TEAEs that occurred at a frequency of $\geq 5\%$ (if no events occurred at the 5% threshold all non-serious TEAEs will be tabulated).

ML39355_STATISTICAL ANALYSIS PLAN_Final 2.0_17 June 2020

This set of tables will be repeated for the following study periods:

- Treatment period defined as first dose of study drug to last dose of study drug in the treatment period + 28 days or until the first dose in the rollover period (Treated Set).

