9.4. Clinical Laboratory Evaluations

eCRF form: “HEMATOLOGY”, “SERUM CHEMISTRY”.

Clinical laboratory evaluations as scheduled in the Table 1 include the following parameters:

- hematology (plasma): white blood cells (WBC) count, red blood cells (RBC) count, hemoglobin, hematocrit, platelet count, (relative) differential WBC count (neutrophils, eosinophils, basophils, monocytes, lymphocytes);
- blood chemistry panel (serum or plasma): albumin, alkaline phosphatase (AP), ALT, AST, direct bilirubin, total bilirubin, total protein, cholesterol, creatine kinase (CK), creatinine, triglycerides, gamma-glutamyl transferase (GGT), glucose, lactic dehydrogenase (LDH), calcium, phosphorus, magnesium, potassium, sodium, urea nitrogen, uric acid;

Creatinine clearance should be assessed at the Screening for eligibility confirmation using the following formula by Cockcroft-Gault (Cockcroft DW et al, 1976):

For serum creatinine concentration in mg/dL:

ML39355_STATISTICAL ANALYSIS PLAN_Final 2.0_17 June 2020

$$\text{CrCl (mL/min)} = (140 - \text{age (years)}) \times \text{weight (kg)} \times 1.0 / 72 \times \text{serum creatinine (mg/dL)}$$

For serum creatinine concentration in $\mu\text{mol/L}$:

$$\text{CrCl (mL/min)} = (140 - \text{age (years)}) \times \text{weight (kg)} \times 1.0 / 0.81 \times \text{serum creatinine } (\mu\text{mol/L})$$

For laboratory parameters the following tables will be presented according to section 7:

- descriptive statistics of measured values and changes from baseline (including creatinine clearance);
- shift tables based on comparison with normal range (Lower/Normal/Higher);
- frequency tables for Out of range: No/Yes clinically significant (Yes CS) / Yes non-clinically significant (Yes NCS) for laboratory parameters.

All laboratory data will be listed.

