Data extracted: DD.MM.YYYY

ML39355_STATISTICAL ANALYSIS PLAN_Final 2.0_17 June 2020
Pregnancies

F. Hoffmann-La Roche Ltd
 ML39355
Table 3.15 Urine pregnancy test
 Treated set (TS)
 Page X of X

	Total (N = XX) n (%)
Screening	
n'	XX
Done [1]	XX (XX.X)
Negative [2]	XX (XX.X)
Positive [2]	XX (XX.X)
Not Done [1]	XX (XX.X)
Male subject [1]	XX (XX.X)
Female subject with no childbearing potential [1]	XX (XX.X)
Other [1]	XX (XX.X)
Day 1	
n'	XX
Done [1]	XX (XX.X)
Negative [2]	XX (XX.X)
Positive [2]	XX (XX.X)
Not Done [1]	XX (XX.X)
Male subject [1]	XX (XX.X)
Female subject with no childbearing potential [1]	XX (XX.X)
Other [1]	XX (XX.X)
...	
...	...

N: the number of women of childbearing potential in the TS. n' - the number of valid observations.

n: the number of patients within a specific category.

[1] Percentages are based on the corresponding number of valid observations.

[2] Percentages are based on the number of patients for whom the pregnancy test was performed.

Path to the program code, date and time of output

Data extracted: DD.MM.YYYY

<The following Urine pregnancy test assessments will be presented: Screening, Day 1, Week 4, Week 8, Week 12, Week 20, Week 26 Day 2>

ML39355_STATISTICAL ANALYSIS PLAN_Final 2.0_17 June 2020
Laboratory tests

 F. Hoffmann-La Roche Ltd
 ML39355

Table 3.16 Hematology. Descriptive statistics

Treated set (TS)

Page X of X

Parameter: XXXXXXXXXXXXXXXXXXXX, <units>

	Total (N = XX)	Change from the baseline
Screening		
n	XX	
Mean	XX.X	
SD	XX.XX	
Median	XX.X	
Min	XX	
Max	XX	
Day 1		
n	XX	
Mean	XX.X	
SD	XX.XX	
Median	XX.X	
Min	XX	
Max	XX	
Baseline		
n	XX	
Mean	XX.X	
SD	XX.XX	
Median	XX.X	
Min	XX	
Max	XX	
Week 2		
n	XX	XX
Mean	XX.X	XX.X
SD	XX.XX	XX.XX
Median	XX.X	XX.X
Min	XX	XX
Max	XX	XX

ML39355_STATISTICAL ANALYSIS PLAN_Final 2.0_17 June 2020

...

...

...

N: the number of patients in the Treated set (TS).
n: the number of valid measurements.

The baseline value for a variable is defined as the last non-missing value collected before the first study drug administration.
<The following assessments will be presented: Screening, Day 1, Baseline, Week 2, Week 4, Week 8, Week 16, Week 20, Week 26 Day 2, Follow-up visit, Week 39, Week 52>
<The following parameters will be presented: Leukocytes ($10^9/L$), Erythrocytes ($10^{12}/L$), Hemoglobin (g/L), Hematocrit (L/L), Platelets ($10^9/L$), Neutrophils/Leukocytes (%), Eosinophils/Leukocytes (%), Basophils/Leukocytes (%), Monocytes/Leukocytes (%), Lymphocytes/Leukocytes (%).>

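### Ten safety table shells leave out the scheduled Week 12 visit; separately, and as a minor improvement, the haematology tables could add an absolute neutrophil count

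*SAP*

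**What the plan says.** **Visits.** Protocol 4.5.13.6 schedules haematology, serum chemistry, vital signs, weight and physical examination at Week 12, and Appendix 1 agrees. Protocol 6.5 requires descriptive summaries of laboratory variables and vital signs at each measurement time point, and laboratory shift tables at each time point. SAP 9.4 opens with "Clinical laboratory evaluations as scheduled in the Table 1 include the following parameters", and SAP 9.5 ties vital signs and physical examination to the same schedule. The note under Table 3.16, however, reads "Week 8, Week 16, Week 20, Week 26 Day 2, Follow-up visit" with no Week 12 in between. Tables 3.18, 3.20, 3.22, 3.23, 3.24 and 3.27 have the same hole. Tables 3.17, 3.19 and 3.21 (chemistry) are to be built like 3.16, 3.18 and 3.20.

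**Neutrophils.** Protocol 4.5.8 collects a white cell count and a "relative) differential WBC count (neutrophils, eosinophils, basophils, monocytes, lymphocytes". Table 3.16 carries leukocytes in 10^9/L and "Neutrophils/Leukocytes (%), Eosinophils/Leukocytes (%), Basophils/Leukocytes" as separate parameters. No section of the SAP multiplies the two. Protocol 5.1.1.5 lists "Agranulocytosis" among the risks seen after authorisation. Reported events are tabulated by preferred term and as "TEAE by maximum severity (Severity, CTCAE v.4.0" (SAP 9.2).

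**The concern.** Change from baseline in laboratory parameters is a named safety endpoint (Protocol section 2; SAP 3.2.4). A programmer who follows the shell notes literally will leave one scheduled on-treatment draw out of every haematology and chemistry table. That includes the liver tests, although liver effects are a named risk (Protocol 5.1.1.3). Week 12 would also be missing for vital signs, weight and physical examination. SAP section 14 says its methods are fully consistent with the protocol, so nothing in the SAP would alert the programmer.

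The neutrophil point is smaller. A low ANC is a property of one patient at one draw. If leukocytes and neutrophil % are summarised separately, the tables do not show whether a low leukocyte count and a low neutrophil % belong to the same patient. A low ANC that the investigator did not report as an adverse event therefore goes uncounted in the tables.

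**Working it through.** **1. Scheduled visits against shell visits.** The schedule is taken from Protocol 4.5.13.5 to 4.5.13.10.

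| Assessment | Scheduled post-baseline | Count | In shell | Missing |
|---|---|---|---|---|
| Haematology, chemistry | W2, 4, 8, 12, 16, 20, 26 (day 2), follow-up, 39, 52 | 10 | 9 | W12 |
| Vital signs, physical examination | W2, 4, 8, 12, 16, 20, 26 (day 1), 26 (day 2), follow-up, 39, 52 | 11 | 10 | W12 |
| Weight | W2, 4, 8, 12, 16, 20, 26 (day 2), follow-up | 8 | 7 | W12 |

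On treatment, 7 laboratory draws are scheduled (W2, 4, 8, 12, 16, 20, 26) and 6 are tabulated. If all 60 planned patients attended every draw, 60 of 60 × 7 = 420 draws would go untabulated: 60/420 = 14.3%. This is an upper figure, since attendance will be lower. The interval between tabulated visits after Week 8 becomes 16 − 8 = 8 weeks instead of 12 − 8 = 4.

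Dropping Week 12 is not a convention of the SAP. Table 3.15 (pregnancy test) lists it, Table 1.4 lists it, and SAP section 7 defines its visit window (days 76 to 86).

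**2. Do the separate tables determine the number of low ANCs?** ANC = leukocytes × neutrophil % / 100. The documents print neither reference limits nor neutrophil cut-offs. The illustration assumes lower limits of 4.0 × 10^9/L and 45% (3.5 and 40% give the same Low counts) and uses 1.0 and 1.5 × 10^9/L as illustrative cut-offs.

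Take one visit with 60 patients, all at 7.0 and 60% at baseline. At the visit 54 are unchanged, with ANC 7.0 × 0.60 = 4.20. Among the other six, the leukocyte values are 3.0, 3.2, 3.4, 7.0, 7.0, 7.0 and the neutrophil values are 30, 33, 36, 60, 60, 60%.

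- Set A pairs low with low: 3.0 × 0.30 = 0.90; 3.2 × 0.33 = 1.06; 3.4 × 0.36 = 1.22; and three at 4.20.
- Set B pairs low with normal: 3.0 × 0.60 = 1.80; 3.2 × 0.60 = 1.92; 3.4 × 0.60 = 2.04; 7.0 × 0.30 = 2.10; 7.0 × 0.33 = 2.31; 7.0 × 0.36 = 2.52.

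Each parameter has the same 60 values in both sets, so Table 3.16 prints the same figures: mean leukocytes (57 × 7.0 + 9.6)/60 = 6.81, minimum 3.0; mean neutrophil % (57 × 60 + 99)/60 = 58.65, minimum 30. SDs, medians, maxima and changes from baseline also agree. Table 3.18 shows three Low leukocyte counts and three Low neutrophil percentages in both.

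| | Set A | Set B |
|---|---|---|
| ANC below 1.0 | 1 | 0 |
| ANC below 1.5 | 3 | 0 |

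The tables do give bounds. No ANC can be below the product of the two minima, 3.0 × 0.30 = 0.90, and at most 3 + 3 = 6 patients carry a Low flag. A patient with no Low flag has ANC of at least 4.0 × 0.45 = 1.80, or 3.5 × 0.40 = 1.40 under the second pair of limits. The clinical-significance flags in Table 3.20 could differ between the sets.

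**The case against.** The case against the neutrophil point is strong. ANC is not a protocol parameter, and no promised analysis is missing. Agranulocytosis is not an adverse event of special interest (Protocol 5.2.3.1), has no row in the protocol's Table 3 management guidance, and is not in the monitoring committee's focus list (5.2.3.2). Protocol 5.3.5.4 requires a laboratory result to be reported as an adverse event on any of four grounds: symptoms, a change in study treatment, an intervention or change in concomitant therapy, or that it "Is clinically significant in the investigator's judgment". Protocol 5.3.5.2 treats neutropenia as a recordable event: "If neutropenia is accompanied by an infection, both events should be reported separately on the eCRF". Listing 30 prints both factors by patient and visit. The illustration rests on assumed values and does not estimate how many unreported low counts to expect. All of this stands, and it makes the ANC summary optional.

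On Week 12, the objection is that SAP 7 and 9.4 already point to the schedule, so the shell notes are a clerical slip and the values would still be listed. That is probably right about the cause. It does not remove the need to correct the notes, which are explicit visit lists that contradict the text they implement.

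A reader might infer three stronger things that the documents do not support:

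- That agranulocytosis could go unseen. Frank cases should be reported as adverse events (Protocol 5.2.2, 5.3.5.4) and would be counted in Tables 3.3.x and graded in 3.7.x.
- That the laboratory tables cannot count low cell counts at all. Table 3.18 counts low leukocytes and low platelets against the normal range; only low absolute neutrophil counts are missing.
- That Week 12 data are lost. Listings 30 and 31 have no visit restriction.

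**Conclusion.** The Week 12 omission is a definite inconsistency between the shells and the protocol. It affects ten tables: 3.16 to 3.24 and 3.27. For laboratory data it removes 1 of 10 post-baseline visits, or 1 of 7 on treatment; the 14.3% of draws assumes full attendance by 60 patients. For laboratory variables and vital signs the omission breaks the commitment in Protocol 6.5. For weight and physical examination the conflict is with the visit schedule in Protocol 4.5.13.6; SAP 9.5 also ties the physical examination output to the schedule. It should be corrected.

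The missing ANC is a minor gap, limited to summarising low neutrophil counts that were not reported as adverse events. That the separate tables cannot supply this count follows from the arithmetic. Its practical size is unknown, because the patient values, reference limits and cut-offs in the illustration are assumptions. The primary analysis and all efficacy endpoints are unaffected.

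**What to change.** 1. Add Week 12 to the assessment lists of Tables 3.16, 3.18, 3.20, 3.22, 3.23, 3.24 and 3.27, and confirm that Tables 3.17, 3.19 and 3.21 follow. The cost is one visit label in seven notes.
2. As an inexpensive improvement, state in SAP 9.4 that ANC = leukocytes × neutrophil % / 100 is derived at every haematology draw. Add it to Table 3.16 and Listing 30. Creatinine clearance, already derived and shown in Table 3.17, is the precedent.
3. Add one Treated-set table of worst post-baseline ANC category by baseline category. The baseline category is needed because, in a single-arm study, a worst-value table alone would mix pre-existing low counts with those that arise on treatment. Use the CTCAE v4.0 cut-offs, print them in the footnote, and check them against the CTCAE text, since neither document prints them.

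No new data are needed. Items 2 and 3 cost one derived variable and one extra table to program and check. SAP section 2 allows revision before database soft lock, so all of this fits in one SAP revision.

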16.2. Figures

No figures are planned in the study.

16.3. Listings

- Listing 1 Disposition: analysis populations
- Listing 2 Disposition: patient visits
- Listing 3 Disposition: violation of inclusion/exclusion criteria
- Listing 4 Disposition: study completion
- Listing 5 Protocol deviations
- Listing 6 Demographic and anthropometric characteristics
- Listing 7 Baseline variables: Surgical lung biopsy (SLB)
- Listing 8 Baseline variables: HRCT scan for patient eligibility confirmation
- Listing 9 Baseline variables: Carbon monoxide diffusing capacity (DLCO)
- Listing 10 Baseline variables: Pre- and post-bronchodilator spirometry parameters
- Listing 11 Baseline variables: Serologic tests
- Listing 12 Baseline variables: GAP assessment
- Listing 13 Review transbronchial lung biopsy/Bronchoalveolar lavage (BAL)
- Listing 14 General medical history
- Listing 15 History of idiopathic pulmonary fibrosis (IPF)
- Listing 16 Prior/concomitant medications
- Listing 17 Prior/concomitant non-drug therapy and procedures
- Listing 18 Spirometry
- Listing 19 6-Minute Walk Test
- Listing 20 Borg scale
- Listing 21 EQ-5D questionnaire
- Listing 22 HRCT scan
- Listing 23 Adverse events
- Listing 24 Exacerbations
- Listing 25 Serious adverse events/Adverse events of special interest
- Listing 26 Study drug administration
- Listing 27 Exposure
- Listing 28 Cases of incorrect administration of study drug / overdose
- Listing 29 Urine pregnancy test
- Listing 30 Hematology
- Listing 31 Blood chemistry
- Listing 32 Vital signs
- Listing 33 ECG
- Listing 34 Physical examinations

ML39355_STATISTICAL ANALYSIS PLAN_Final 2.0_17 June 2020

F. Hoffmann-La Roche Ltd
ML39355

Listing 1 Disposition: analysis populations
All Enrolled patients
Page X of X

Patient ID/ Sex/ Age (years)/ Race	Date, Time of informed consent signature	The Allocated to treatment set	Participation in the rollover study	The Treated set (TS)	The Full analysis set (FAS)	Complete case set (CCS)	Reason for missing 26 week FVC data	Treatment until Week 26
XXXXXXXX/ X/ XX/ XXXXX	YYYY-MM-DD HH:MM	Yes	Yes	Yes	Yes	Yes		Yes
XXXXXXXX/ X/ XX/	YYYY-MM-DD HH:MM	Yes	No	Yes	No	No	Death	No
XXXXXXXX/ X/ XX/	YYYY-MM-DD HH:MM	No	No	No	No	No	Discontinuation Lung transplantation	No No
...								

Path to the program code, date and time of output

Data extracted: DD.MM.YYYY

ML39355_STATISTICAL ANALYSIS PLAN_Final 2.0_17 June 2020

F. Hoffmann-La Roche Ltd
ML39355

Listing 2 Disposition: patient visits
All Enrolled patients
Page X of X

Patient ID/ Sex/ Age (years)/ Race	Visit	Visit within visit window	Date / Study day	Main reason for unscheduled visit
XXXXXXXX/ X/ XX/ XXXXX	XXXXXX	Yes	YYYY-MM-DD/ XX	
	XXXXXX	No	YYYY-MM-DD/ XX	
	XXXXXX		YYYY-MM-DD/ XX	XXXXXXXXXXXX XXXXXXXXXXXX
...				

Path to the program code, date and time of output

Data extracted: DD.MM.YYYY

ML39355_STATISTICAL ANALYSIS PLAN_Final 2.0_17 June 2020

F. Hoffmann-La Roche Ltd
ML39355

Listing 4 Disposition: study completion
All Enrolled patients
Page X of X

Patient ID/ Sex/ Age (years)/ Race	Date of study completion or discontinuation/ Study day	End of study status	Main reason for premature study termination
XXXXXXXX/ X/ XX/ XXXXX	YYYY-MM-DD/ XX	Discontinued	XXXXXXXXXXXXXXXXXXXXXXXXXXXXXXXXXXXX
XXXXXXXX/ X/ XX/ XXXXX	YYYY-MM-DD/ XX	Discontinued	Other: XXXXXXXXXXXXXXXXXXXXXXXX
XXXXXXXX/ X/ XX/ XXXXX	YYYY-MM-DD/ XX	Completed	
XXXXXXXX/ X/ XX/ XXXXX	YYYY-MM-DD/ XX	Screening failure	Presence or development of Inclusion/Exclusion criterion (-a): XXXXX
...			

Path to the program code, date and time of output

Data extracted: DD.MM.YYYY

ML39355_STATISTICAL ANALYSIS PLAN_Final 2.0_17 June 2020

F. Hoffmann-La Roche Ltd
ML39355

Listing 5 Protocol deviations

All Enrolled patients
Page X of X

Patient ID/ Sex/ Age (years)/ Race	Date of deviation revealed / Study day	Visit name	Form name	Description of deviation
XXXXXXXX/ X/ XX/ XXXXX	YYYY-MM-DD / XX	XXXXX	XXXXX	XXXXXXXXXXXXXXXXXXXXXXXXXXXX
XXXXXXXX/ X/ XX/ XXXXX	YYYY-MM-DD / XX	XXXXX	XXXXX	XXXXXXXXXXXXXXXXXXXXXXXXXXXX
XXXXXXXX/ X/ XX/ XXXXX	YYYY-MM-DD / XX	XXXXX	XXXXX	XXXXXXXXXXXXXXXXXXXXXXXXXXXX
...				

Path to the program code, date and time of output

Data extracted: DD.MM.YYYY

ML39355_STATISTICAL ANALYSIS PLAN_Final 2.0_17 June 2020

F. Hoffmann-La Roche Ltd
ML39355

Listing 6 Demographics and anthropometric characteristics
All Patients
Page X of X

Patient ID/ Sex/ Age (years)/ Race	Date of birth	Age, years	Sex	Race	Ethnicity	Weight, kg	Height, cm	BMI, kg/m2
XXXXXXXX/ X/ XX/ XXXXX	YYYY-MM-DD	XXXXX	XXXXX	XXXXX	XXXXX	XX	XXX	XX.X
XXXXXXXX/ X/ XX/ XXXXX	YYYY-MM-DD	XXXXX	XXXXX	XXXXX	XXXXX	XX	XXX	XX.X
XXXXXXXX/ X/ XX/ XXXXX	YYYY-MM-DD	XXXXX	XXXXX	XXXXX	XXXXX	XX	XXX	XX.X
...								

Path to the program code, date and time of output

Data extracted: DD.MM.YYYY

ML39355_STATISTICAL ANALYSIS PLAN_Final 2.0_17 June 2020

F. Hoffmann-La Roche Ltd
ML39355

Listing 7 Baseline variables: Surgical lung biopsy (SLB)
All Enrolled patients
Page X of X

Patient ID/ Sex/ Age (years)/ Race	Date of sample collection/ Study day	Assessment of regional specialist: UIP Pattern	Assessment of central specialist: UIP Pattern
XXXXXXXX/ X/ XX/ XXXX	YYYY-MM-DD/ XX	XXXXXXXXXXXXXXXXXXXXXXXXXXXX	XXXXXXXXXXXXXXXXXXXXXXXXXXXX
XXXXXXXX/ X/ XX/ XXXX	YYYY-MM-DD/ XX	XXXXXXXXXXXXXXXXXXXXXXXXXXXX	XXXXXXXXXXXXXXXXXXXXXXXXXXXX
XXXXXXXX/ X/ XX/ XXXX	YYYY-MM-DD/ XX	XXXXXXXXXXXXXXXXXXXXXXXXXXXX	XXXXXXXXXXXXXXXXXXXXXXXXXXXX
...			

Path to the program code, date and time of output

Data extracted: DD.MM.YYYY

ML39355_STATISTICAL ANALYSIS PLAN_Final 2.0_17 June 2020

F. Hoffmann-La Roche Ltd
ML39355

Listing 8 Baseline variables: HRCT scan for patient eligibility confirmation
All Enrolled patients
Page X of X

Patient ID/ Sex/ Age (years)/ Race	Date of HRCT scan/ Study day	Assessment of regional specialist: UIP Pattern	Assessment of central specialist (1): UIP Pattern	Assessment of central specialist (2): UIP Pattern or Not performed	Reasons if Not Done
XXXXXXXX/ X/ XX/ XXXXX	YYYY-MM-DD/ XX	XXXXXXXXXXXXXXXXXXXXX	XXXXXXXXXXXXXXXXXXXXX	XXXXXXXXXXXXXXXXXXXXX	
XXXXXXXX/ X/ XX/ XXXXX	YYYY-MM-DD/ XX	XXXXXXXXXXXXXXXXXXXXX	XXXXXXXXXXXXXXXXXXXXX	XXXXXXXXXXXXXXXXXXXXX	
XXXXXXXX/ X/ XX/ XXXXX	YYYY-MM-DD/ XX	XXXXXXXXXXXXXXXXXXXXX	XXXXXXXXXXXXXXXXXXXXX	XXXXXXXXXXXXXXXXXXXXX	
...					

Path to the program code, date and time of output

Data extracted: DD.MM.YYYY

ML39355_STATISTICAL ANALYSIS PLAN_Final 2.0_17 June 2020

F. Hoffmann-La Roche Ltd
ML39355

Listing 9 Baseline variables: Carbon monoxide diffusing capacity (DLCO)
All Enrolled patients
Page X of X

Patient ID/ Sex/ Age (years)/ Race	Date, Time of assessment/ Study day	Date, Time of Hb assessment/ Study day	Hb value	Hb units	Parameter	DLCO result, %
XXXXXXXX/ X/ XX/ XXXXX	YYYY-MM-DD HH:MM/ XX				Predicted DLCO	XXXXX
		YYYY-MM-DD HH:MM/ XX	XX	XXXXX	Hb-corrected DLCO	XXXXX
XXXXXXXX/ X/ XX/ XXXXX	YYYY-MM-DD HH:MM/ XX				Predicted DLCO	XXXXX
		YYYY-MM-DD HH:MM/ XX	XX	XXXXX	Hb-corrected DLCO	XXXXX
...						

Path to the program code, date and time of output

Data extracted: DD.MM.YYYY

ML39355_STATISTICAL ANALYSIS PLAN_Final 2.0_17 June 2020

F. Hoffmann-La Roche Ltd
ML39355

Listing 10 Baseline variables: Pre- and post-bronchodilator spirometry parameters
All Enrolled patients
Page X of X

Patient ID/ Sex/ Age (years)/ Race	Date of assessment/ Study day	Time of assessment	Period of assessment	Parameter	Result	Units	Reason if Not Done
XXXXXXXX/ X/ XX/ XXXXX	YYYY-MM-DD/ XX	HH:MM	Before bronchodilator administration	FVC (absolute)	XXX	mL	
				FVC (relative) predicted FEV1/FVC	XXX XX.X	%	
		HH:MM	After bronchodilator administration		
				FVC (absolute)	XXX	mL	
XXXXXXXX/ X/ XX/ XXXXX	YYYY-MM-DD/ XX	HH:MM	Before bronchodilator administration	FVC (absolute)	Not Done		XXXX XX XXXXXXXX
					
		HH:MM	After bronchodilator administration	FVC (absolute)	XXX	mL	
					
...							

Path to the program code, date and time of output

Data extracted: DD.MM.YYYY

ML39355_STATISTICAL ANALYSIS PLAN_Final 2.0_17 June 2020

F. Hoffmann-La Roche Ltd
ML39355

Listing 11 Baseline variables: Serologic tests

All Enrolled patients
Page X of X

Patient ID/ Sex/ Age (years)/ Race	Date, Time of assessment/ Study day	Lab Test	Fasting Status	Result	Reason if Not Done
XXXXXXXX/ X/ XX/ XXXXX	YYYY-MM-DD HH:MM/ XX	Rheumatoid factor	Yes	XXXXX	
		Anticyclic citrullinated peptide	Yes	XXXXX	
		Antinuclear antibody titer		Not Done	XXXXXXXXXXXXXXXXXXXX
XXXXXXXX/ X/ XX/ XXXXX	YYYY-MM-DD HH:MM/ XX	Rheumatoid factor	No	XXXXX	
		Anticyclic citrullinated peptide	No	XXXXX	
		Antinuclear antibody titer	No	XXXXX	
...					

Path to the program code, date and time of output

Data extracted: DD.MM.YYYY

ML39355_STATISTICAL ANALYSIS PLAN_Final 2.0_17 June 2020

F. Hoffmann-La Roche Ltd
ML39355

Listing 12 Baseline variables: GAP assessment
All Enrolled patients
Page X of X

Patient ID/ Sex/ Age (years)/ Race	Date of assessment/ Study day	FVC, %, predicted	Dlco, %, predicted	Stage/ GAP Index	Mortality (1-y)	Mortality (2-y)	Mortality (3-y)	Reason if Not Done
XXXXXXXX/ X/ XX/ XXXXX	YYYY-MM-DD/ XX	XXXXX	XXXXX	X/XXXXX	XXXXX	XXXXX	XXXXX	XXXXXXXXXX
XXXXXXXX/ X/ XX/ XXXXX	YYYY-MM-DD/ XX	XXXXX	XXXXX	X/XXXXX	XXXXX	XXXXX	XXXXX	XXXXXXXXXX
XXXXXXXX/ X/ XX/ XXXXX	YYYY-MM-DD/ XX	XXXXX	XXXXX	X/XXXXX	XXXXX	XXXXX	XXXXX	XXXXXXXXXX
...								

Path to the program code, date and time of output

Data extracted: DD.MM.YYYY

ML39355_STATISTICAL ANALYSIS PLAN_Final 2.0_17 June 2020

F. Hoffmann-La Roche Ltd
ML39355

Listing 13 Review transbronchial lung biopsy/ Bronchoalveolar lavage (BAL)
All Enrolled patients
Page X of X

Patient ID/ Sex/ Age (years)/ Race	Visit	Medical procedure	Date of sample collection/ Study day	Are there features supporting an alternative diagnosis?	Comments if Yes	Result
XXXXXXXX/ X/ XX/ XXXXXX	XXXXXXXX	Transbronchial biopsy	YYYY-MM-DD/ XX	XXXXX	XXXXXXXXXXXXXXXXXXXXX XXXXXXXXXXXXXXXXXXXXX	XXXXXXXXXXXXXXXXXXXXX XXXXXXXXXXXXXXXXXXXXX
		Bronchoalveolar lavage (BAL)	YYYY-MM-DD/ XX	XXXXX	XXXXXXXXXXXXXXXXXXXXX XXXXXXXXXXXXXXXXXXXXX	XXXXXXXXXXXXXXXXXXXXX XXXXXXXXXXXXXXXXXXXXX
XXXXXXXX/ X/ XX/ XXXXXX	XXXXXXXX	Transbronchial biopsy	YYYY-MM-DD/ XX	XXXXX	XXXXXXXXXXXXXXXXXXXXX XXXXXXXXXXXXXXXXXXXXX	XXXXXXXXXXXXXXXXXXXXX XXXXXXXXXXXXXXXXXXXXX
		Bronchoalveolar lavage (BAL)	YYYY-MM-DD/ XX	XXXXX	XXXXXXXXXXXXXXXXXXXXX XXXXXXXXXXXXXXXXXXXXX	XXXXXXXXXXXXXXXXXXXXX XXXXXXXXXXXXXXXXXXXXX
XXXXXXXX/ X/ XX/ XXXXXX	XXXXXXXX	Transbronchial biopsy	YYYY-MM-DD/ XX	XXXXX	XXXXXXXXXXXXXXXXXXXXX XXXXXXXXXXXXXXXXXXXXX	XXXXXXXXXXXXXXXXXXXXX XXXXXXXXXXXXXXXXXXXXX
		Bronchoalveolar lavage (BAL)	YYYY-MM-DD/ XX	XXXXX	XXXXXXXXXXXXXXXXXXXXX XXXXXXXXXXXXXXXXXXXXX	XXXXXXXXXXXXXXXXXXXXX XXXXXXXXXXXXXXXXXXXXX
...						

Path to the program code, date and time of output

Data extracted: DD.MM.YYYY

ML39355_STATISTICAL ANALYSIS PLAN_Final 2.0_17 June 2020

F. Hoffmann-La Roche Ltd
ML39355

Listing 15 History of idiopathic pulmonary fibrosis (IPF)
All Enrolled patients
Page X of X

Patient ID/ Sex/ Age (years)/ Race	Diagnosis	Duration of clinical symptoms consistent with IPF (in months)	Clinically significant environmental exposure known to cause pulmonary fibrosis	Known explanation for interstitial lung disease	Cigarette smoking within 28 days before the treatment start
XXXXXXXX/ X/ XX/ XXXXX	Idiopathic Pulmonary Fibrosis	XX	Yes	No	Yes
XXXXXXXX/ X/ XX/ XXXXX	Idiopathic Pulmonary Fibrosis	XX	Yes	No	No
XXXXXXXX/ X/ XX/ XXXXX	Idiopathic Pulmonary Fibrosis	XX	No	Yes	Yes
...					

Path to the program code, date and time of output

Data extracted: DD.MM.YYYY

ML39355_STATISTICAL ANALYSIS PLAN_Final 2.0_17 June 2020

F. Hoffmann-La Roche Ltd
ML39355

Listing 16 Prior/concomitant medications
All Enrolled patients
Page X of X

Patient ID/ Sex/ Age (years)/ Race	1st Lvl, Anatomical main group/ 2nd Lvl, Therapeutic subgroup/ 3rd Lvl, Pharmacological subgroup/ 4th Lvl, Chemical subgroup/ 5th Lvl, Chemical substance/ Medication	Prior/ Concomitant	Start date, Time/ Study day/ Stop date, Time/ Study day	Dose (Units)/ Frequency/ Route	Indication for use	Comments
XXXXXXXX/ X/ XX/ XXXXX	XXXXXXXXXXXXXXXXXXXXXXXXXXXXXXXXXXXX/ XXXXXXXXXXXXXXXXXXXXXXXXXXXXXXXXXXXX/ XXXXXXXXXXXXXXXXXXXXXXXXXXXXXXXXXXXX/ XXXXXXXXXXXXXXXXXXXXXXXXXXXXXXXXXXXX/ XXXXXXXXXXXXXXXXXXXXXXXXXXXXXXXXXXXX/ XXXXXXXXXXXXXXXXXXXXXXXXXXXXXXXXXXXX	P	YYYY-MM-DD HH:MM/ XX/ YYYY-MM-DD HH:MM/ XX	XXXXX (XXXXX) / XXXXX/ XXXXX	XXXXXXXXXXXXX	XXXXXXXXXXXXX
XXXXXXXX/ X/ XX/ XXXXX	XXXXXXXXXXXXXXXXXXXXXXXXXXXXXXXXXXXX/ XXXXXXXXXXXXXXXXXXXXXXXXXXXXXXXXXXXX/ XXXXXXXXXXXXXXXXXXXXXXXXXXXXXXXXXXXX/ XXXXXXXXXXXXXXXXXXXXXXXXXXXXXXXXXXXX/ XXXXXXXXXXXXXXXXXXXXXXXXXXXXXXXXXXXX/ XXXXXXXXXXXXXXXXXXXXXXXXXXXXXXXXXXXX	C	YYYY-MM-DD HH:MM/ XX/ Ongoing	XXXXX (XXXXX) / XXXXX/ XXXXX	XXXXXXXXXXXXX	XXXXXXXXXXXXX
...						

P=Prior, C=Concomitant.
Medications are coded using WHODD version XX.X.

Path to the program code, date and time of output

Data extracted: DD.MM.YYYY

ML39355_STATISTICAL ANALYSIS PLAN_Final 2.0_17 June 2020

F. Hoffmann-La Roche Ltd
ML39355

Listing 17 Prior/concomitant non-drug therapy and procedures
All Enrolled patients
Page X of X

Patient ID/ Sex/ Age (years)/ Race	System Organ Class/ Preferred Term/ Lowest Level Term/ Treatment	Prior/ Concomitant	Start date, Time/ Study day/ Stop date, Time/ Study day	Indication	Comments
XXXXXXXX/ X/ XX/ XXXXX	XX/ XX/ XX/ XX	P	YYYY-MM-DD HH:MM/ XX/ YYYY-MM-DD HH:MM/ XX	XXXXXXXXXXXXXXXXXXXX	XXXXXXXXXXXX
...					

Non-drug therapy and procedures are coded using MedDRA version XX.X.

Path to the program code, date and time of output

Data extracted: DD.MM.YYYY

ML39355_STATISTICAL ANALYSIS PLAN_Final 2.0_17 June 2020

F. Hoffmann-La Roche Ltd
ML39355
Listing 18 Spirometry
All Enrolled patients
Page X of X

Patient ID/ Sex/ Age (years)/ Race	Visit	Date, Time of assessment/ Study day	Parameter	Result	Units	Change from baseline/Base line	Reason if Not Done	
XXXXXXXX/ X/ XX/ XXXXX	Screening/Retrospe ctive values	YYYY-MM-DD/ XX	FVC (absolute)	XXXXXX	mL			
			FVC (relative) predicted	XXXXXX	%			
		YYYY-MM-DD/ XX	FVC (absolute)	XXXXXX	mL			
			FVC (relative) predicted	XXXXXX	%			
		...	YYYY-MM-DD/ XX	FVC (absolute)	XXXXXX	mL		
				FVC (relative) predicted	XXXXXX	%		
	Day 1	YYYY-MM-DD HH:MM/ XX	FVC (absolute)	XXXXXX	mL			
			FVC (relative) predicted	XXXXXX	%			
	Week 12	YYYY-MM-DD HH:MM/ XX	FVC (absolute)	Not Done			XXXXXXXXXX	
			FVC (relative) predicted	XXXXXX	%	XXXXXX/XXXXXX		
	Week 26	YYYY-MM-DD/ XX	FVC (absolute)	XXXXXX	mL	XXXXXX/XXXXXX		
			FVC (relative) predicted	XXXXXX	%	XXXXXX/XXXXXX		
...		

ML39355_STATISTICAL ANALYSIS PLAN_Final 2.0_17 June 2020

Path to the program code, date and time of output

Data extracted: DD.MM.YYYY

<For screening list values before bronchodilator administration only.>

ML39355_STATISTICAL ANALYSIS PLAN_Final 2.0_17 June 2020

F. Hoffmann-La Roche Ltd
ML39355

Listing 19 6-Minute Walk Test

All Enrolled patients
Page X of X

Patient ID/ Sex/ Age (years)/ Race	Visit	Date of assessment / Study day	Result, m	Change from Baseline/Baseline	Reason if Not Done
XXXXXXXX/ X/ XX/ XXXXX	XXXXX	YYYY-MM-DD / XX	XXXXX	XXXXX/XXXXX	
	XXXXX	YYYY-MM-DD / XX	XXXXX	XXXXX/XXXXX	
	XXXXX	YYYY-MM-DD / XX	XXXXX	XXXXX/XXXXX	
...					

Path to the program code, date and time of output

Data extracted: DD.MM.YYYY

ML39355_STATISTICAL ANALYSIS PLAN_Final 2.0_17 June 2020

F. Hoffmann-La Roche Ltd
ML39355

Listing 20 Borg scale
All Enrolled patients
Page X of X

Patient ID/ Sex/ Age (years)/ Race	Visit	Date of assessment/ Study day	Timepoint	Time of assessment	Result	Change from Pre- test Baseline/ Pre-test Baseline	Change from Baseline/ Baseline	Reason if Not Done
XXXXXXXX/ X/ XX/ XXXXX	XXXXX XXX	YYYY-MM-DD/ XX	Before the 6- minute exercise	HH:MM	XXXXX			
			After the 6- minute exercise	HH:MM	XXXXX	XXXXX/XXXXX		
	XXXXX XX	YYYY-MM-DD/ XX	Before the 6- minute exercise	HH:MM	XXXXX		XXXXX/XXXXX	
			After the 6- minute exercise	HH:MM	XXXXX	XXXXX/XXXXX		
...								

Path to the program code, date and time of output

Data extracted: DD.MM.YYYY

ML39355_STATISTICAL ANALYSIS PLAN_Final 2.0_17 June 2020

F. Hoffmann-La Roche Ltd
ML39355

Listing 21 EQ-5D-5L questionnaire

All Enrolled patients
Page X of X

Patient ID/ Sex/ Age (years)/ Race	Visit	Date, Time of assessment/ Study day	Mobility/ Self-care/ Usual activities/ Pain/Discomfort/ Anxiety/Depression	Your own health state today (VAS) / Change from Baseline/ Baseline	Index score/ Change from Baseline/ Baseline	Reason if Not Done
XXXXXXXX/ X/ XX/ XXXXX	XXXXX	YYYY-MM-DD HH:MM/ XX	XX/ XX/ XX/ XX/ XX	XXXXX/XXXX/XXXX	XXXXX/XXXX/XXXX	XXXXXXXXXXXXXXXXXXXX
...						

Path to the program code, date and time of output

Data extracted: DD.MM.YYYY

ML39355_STATISTICAL ANALYSIS PLAN_Final 2.0_17 June 2020

F. Hoffmann-La Roche Ltd
ML39355
Listing 22 HRCT scan
All Enrolled patients
Page X of X

Patient ID/ Sex/ Age (years)/ Race	Visit	Date of HRCT scan / Study day	Parameter	Result	Change from Baseline/Baseline	Reason if Not Done
XXXXXXXX/ X/ XX/ XXXXX	XXXXX	YYYY-MM-DD / XX	HRCT fibrosis score	XXXXX	XXXXX/XXXXX	
			Ground-glass opacity	XXXXX	XXXXX/XXXXX	
	XXXXX	YYYY-MM-DD / XX	HRCT fibrosis score	XXXXX	XXXXX/XXXXX	
			Ground-glass opacity	Not Done		XXXXXXXXXXXXXXXXXXXXX
...						

Path to the program code, date and time of output

Data extracted: DD.MM.YYYY

ML39355_STATISTICAL ANALYSIS PLAN_Final 2.0_17 June 2020

F. Hoffmann-La Roche Ltd
ML39355

Listing 23 Adverse events

